Bridging animal and human models of exercise-induced  
visual rehabilitation

NCT02911805

May 5, 2023

**Specific Aim:** Assess visual outcomes and serum BDNF **in human subjects** before, during, and after an aerobic exercise training program that includes progressive increases in exercise. **Hypothesis:** Circulating BDNF will increase and visual outcomes will change with increasing exercise intensity or interval.

**Objectives:** To assess changes in visual acuity (primary outcome) and contrast sensitivity (secondary outcome) and to determine the feasibility of and to develop expertise in measuring BDNF in human blood samples (tertiary outcome). **Rationale:** Animal and human studies examining the effects of exercise on cognition and peripheral nerve regeneration demonstrate that circulating BDNF levels vary with outcome; whether BDNF varies with exercise levels is less well studied. If amounts of exercise and circulating BDNF levels similarly co-vary in humans and in mice, BDNF may be useful as a biomarker for testing exercise regimens as interventions in human studies. Additionally, no human studies have monitored exercise, BDNF, and retinal and visual outcomes. **Design:** The study is comprised of a 12-week exercise portion with one return visit 3 months after the end of the exercise portion. Participants will be recruited from our volunteer database, which includes elderly individuals (65-89 years old) who are not visually impaired and who report being sedentary (defined as engaging in structured physical activity for 30 minutes or less over the last 3 months) and who meet other inclusion criteria previously established for our exercise studies. Participants will be divided into a group that will exercise and a group that will remain sedentary. Exercising participants will train three times a week for 12 weeks on a stationary bicycle ergometer ("spin" training). Exercise intensity will begin at low levels (50% of maximal heart rate reserve) and will be increased by 5% every week (as tolerated by the participant) to a maximum of 80% of maximal heart rate. Exercise time will progress from an initial 20 minutes per session to a maximum of 45 minutes by increasing 5 minutes each week. A CPR-certified fitness specialist will monitor each session. We will follow the guidelines provided by the American College of Sports Medicine for optimizing cardiovascular fitness. Blood draws and visual assessments will be taken at one week prior to the 12-week regimen, at the 3-month follow-up, and at weeks 1, 4, 8, and 12 of the 12-week regimen. Blood will be drawn by a certified phlebotomist in the rest period before the exercise, immediately following the exercise, and after a recovery period of 10 min. Visual assessment will include visual acuity and contrast sensitivity (CSV-1000E). Control (non-exercising) participants will have blood drawn and undergo other assessments identically to the exercised participants. To control for potential benefits of the spinning program that are unrelated to aerobic exercise, they will participate in group balance training. All participants will be instructed to otherwise continue with their daily routines and will be contacted bi-weekly to track self-reported levels of physical activity outside of the study. All participants will be asked to return to their pre-study routines following the 12-week exercise portion of the study. All procedures involving human subjects have been reviewed and approved by an Institutional Review Board (IRB). Sample remainders will be archived for analyses that are beyond the scope of a SPiRE support. **Expected outcomes and Significance:** If functional changes differ between exercised versus control cohorts across the study period, we will conclude that even relatively short-term aerobic exercise can be beneficial to visual health. Such an outcome would also suggest that effects are due to physiological mechanisms rather than test-specific psychological confounds. Circulating levels of BDNF will be measurable and will increase in exercised versus unexercised subjects, indicating that circulating BDNF levels correlate with exercise activity. **Potential difficulties and alternative approaches:** (1) It may be that changes in BDNF levels are not observed. Human studies demonstrate that many forms of aerobic exercise, including "spin" ergometer training, increase circulating BDNF levels. However, the temporal relationship between an exercise session and its effects on BDNF may vary. If we do not observe changes in BDNF with the proposed sampling regimen within the first week of the 12-week training portion of the study, we will add a draw at the midway point of the spin session. Additional draws during the recovery period at 5 min intervals may be attempted (we have institutional approval, though these would require cannulation, which increases complexity and increases the probability of participant drop-out). Additions will be iterative and kept to a minimum based on assaying for BDNF concentration the day of the spin sessions. (2) It may be that that BDNF levels do not vary with exercise volume changes. If so, similar to the suggested alternative in Aim 1, additional circulating growth factors will be assessed. Candidates include insulin-like growth factor 1 (IGF-1), vascular endothelial growth factor (VEGF), and leukemia insulin factor (LIF), nerve growth factor (NGF), and Neurotrophin-4/5.

## Methods

### *Visual function testing:*

**Visual acuity:** The visual acuity of the subjects will be measured according to a standard procedure developed and used by many multi-center clinical trials. An Early Treatment Diabetic Retinopathy Study (ETDRS) Chart and a 3 meter testing lane providing standardized chart illumination (80 to 120 cd/m^2) are used to test visual acuity. Testing is done at a distance of 3 meters (20 feet) or (for subjects with sufficiently reduced vision) a distance of 1 meter. The 3 meter distance should be marked clearly and permanently while the 1 meter distance must be measured with a 1 meter string. Subjects should be prevented from seeing the chart until the visual acuity testing actually begins.

The subject is first positioned at 3 meters in a chair with his or her back firmly touching the back of the chair. The head of the subject should not move forward or backward during the test so that the subject's eyes remain at the specified distance. The subject is instructed to slowly read with the study eye(s) each letter of each line at a rate not faster than about one letter per second. If the subject is unable to correctly identify all the letters of the top two lines, then position the subject at 1 meter and again instruct the subject to read each letter of each line beginning again with the top line. If the subject loses his or her place the examiner may point to a line (but outside the line at the edge of the chart) or below the letter (at a distance equal to the inter-letter spacing in a line) with a long pointer. The testing procedure for visual acuity is based on the principle that the objective is to test resolution ability and not the ability to find each letter on a line.

The subject's responses are recorded on the visual acuity recording sheet. Each wrong response is scored by putting an X through the letter and writing the incorrect response above the letter. Once a subject has identified a letter with a definite single-letter response and has read the next letter, a correction of the previous letter cannot be accepted. If the subject changes a response before s/he has read aloud the next letter, then the change should be accepted. When the subject has missed at least 3 letters on the previous line and can make no further meaningful guesses, despite urges to read or guess, the examiner should stop the test for that eye. The examiner records the number of letters correctly read and from this number computes the Snellen Equivalent and LogMAR values from the table provided.

**Script: This is a visual acuity test like you might have seen at your doctor's office. This chart shows letters that become smaller toward the bottom. I want you to stop at the end of each row and wait until I ask you to continue. Please try your best to read all the letters. If you are unsure, I will ask you to take a guess even if it is very difficult for you to see. Any questions?**

**Statistical analysis:** The number of correct ETDRS responses from a subject assessed prior to start of the first session of the the 12 week study is subtracted from the number of correct responses elicited at the end of the last session of the study. The means of these differences for each study group (Balance Training vs Aerobic Exercise) is compared by two-tailed t-test.

**Contrast sensitivity:** The contrast sensitivity of the subjects will be measured with the Pelli-Robson Chart following the instructions provided with the chart. The two sides of the Pelli-Robson Chart have different letter sequences but are otherwise identical. The chart should be illuminated as uniformly as possible, so that the luminance of the white areas is between 80 and 120 cd/ m^2 with no glare. The patient should sit directly in front of the chart at a distance of 1 meter (use the same 1 meter string as for visual acuity testing to measure the eye-to-chart distance). Subjects should be prevented from seeing the chart until the contrast sensitivity testing actually begins. Subjects should wear their best distance correction.

As in visual acuity testing, the subject is instructed to slowly read with their study eye(s) each letter of each line at a rate not faster than about one letter per second. If the subject loses his or her place the examiner may point to a line (but outside the line at the edge of the chart) or below the letter (at a distance equal to the inter-letter spacing in a line) with a long pointer. The testing procedure for contrast sensitivity is also based on the principle that the objective is to test threshold contrast sensitivity and not the ability to find each letter on a line.

The subject's responses are recorded on the contrast sensitivity recording sheet. Each wrong response is scored by putting an X through the letter and writing the incorrect response above the letter. Once a subject has identified a letter with a definite single-letter response and has read the next letter, a correction of the previous letter cannot be accepted. If the subject changes a response before s/he has read aloud the next letter, then the change should be accepted. When the subject says s/he cannot read a letter, s/he should be encouraged to guess. If the subject identifies a letter as one of two or more letters, s/he should be asked to choose one letter. When the subject has missed at least 2 letters of the previous triplet and can make no further meaningful guesses, despite urges to read or guess, the examiner should stop the test for that eye.

The examiner records the number of letters correctly read and from this number computes the Contrast Sensitivity from the table provided.

Excerpt containing one possible script (per Pelli Robson instruction manual): *Explaining the test*. This test will be unfamiliar to most of your patients, and they may cooperate more readily if they understand why it is being performed. Here is one possible set of instructions. **In everyday life we do not look at small black objects. Contrast sensitivity is a more realistic assessment of how well we see large faint objects around us. This chart is a little different from the regular eye chart. With this chart letters are all uniformly large, and they fade out towards the bottom of the chart. The top line has high-contrast letters, black on white. The letters below them are grey and more difficult to see, very much like looking through fog or dirty glasses. What you must do is read as many letters as you can. The letters at the bottom of the chart are difficult for everyone to read, so do not be discouraged.** When the patient begins to have trouble, it may be useful to provide some strategies to help him or her make the best attempt at seeing the letters. **Try reading just one letter at a time. Try blinking, or viewing the letter a little eccentrically, moving your head from side to side. Indicate (without touching the chart) the particular letter you want the patient to concentrate on. Try reading this one. Do you see something against the white background? Is there a smudge? Is it round or square? Does it have corners or lines you can see? Keep trying. The whole letter may suddenly appear to you. Go ahead and guess.**

**Serum BDNF analysis:** Blood is collected into 2 ml microtubes containing serum separation gel. The blood is allowed to clot for 30 min. Serum is then separated by centrifugation. Enzyme linked immusorbant assay (ELISA) is used to quantify BDNF in a set volume of serum from each sample. Briefly, highly specific antibodies against BDNF are used to bind BDNF to a 96 well plate surface and to link horseradish peroxidase (HRP) to the bound BDNF. The quantity of BDNF is indirectly measured by the activity of the HRP that is bound to the plate surface using a HRP substrate that produces a blue dye when catalyzed. A plate reader is used to measure absorbance at 450 nm (BioTek ELx808), and absorbance values were compared with an internal standard curve on the same plate.

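### No masking of the vision examiner is described, and the examiner decides how much to urge and when to stop, so arm-dependent prompting could enter the acuity change score

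*Combined protocol and SAP*

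**What the plan says.** The Objectives name visual acuity as the primary outcome and contrast sensitivity as the secondary one. Under Visual acuity, Statistical analysis, the letters read correctly before the first session form the baseline, which "is subtracted from the number of correct responses elicited at the end of the last session of the study". Then: "The means of these differences for each study group (Balance Training vs Aerobic Exercise) is compared by two-tailed t-test".

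One role produces that number: "The examiner records the number of letters correctly read and from this number computes the Snellen Equivalent and LogMAR values". The stopping rule for acuity has two parts, and both must be met. The first can be counted: at least three letters missed on the previous line. The second is a judgement, that the subject "can make no further meaningful guesses, despite urges to read or guess, the examiner should stop the test for that eye". An opening script is given, but no number or wording of later urges.

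Contrast sensitivity has a similar rule: "When the subject has missed at least 2 letters of the previous triplet and can make no further meaningful guesses", the examiner ends the test. For this test only, the plan reproduces part of the chart's manual as one possible script. It adds that, for a patient in difficulty, "it may be useful to provide some strategies to help him or her make the best attempt at seeing the letters", and lists several hints.

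The documents do not say who tests vision, whether that person knows the arm, or whether anyone else scores the sheets. Under Expected outcomes and Significance, a difference between cohorts is said to suggest that "effects are due to physiological mechanisms rather than test-specific psychological confounds".

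**The concern.** Missing three letters is necessary but not sufficient to stop. After that, further letters depend on how long the examiner keeps asking, and each extra guess can only hold or raise the count. If the examiner expects exercise to help and knows who exercised, more urging in that arm adds letters there. The t-test cannot tell those letters from an effect of exercise.

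The timing matters. Baseline is taken before the first session. The final count is taken at the end of the last one, so the participant may come straight from spin or balance training. Prompting that differed by arm equally at both visits would cancel in the change score; prompting that differs only at the end would not.

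Two things are at stake: the error rate of the primary comparison, and the inference drawn from it. Examiner expectation is a psychological influence specific to the test, which is the kind of explanation the plan says a group difference would argue against.

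**Working it through.** **Figure to reproduce.** There is none. The documents give no sample size, alpha, SD, allocation ratio or target difference. What follows is a sensitivity calculation.

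**Inputs from the plan.** Outcome: change in letters correct. Test: two-sample t-test of mean change, two-tailed.

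**Inputs assumed.** Alpha 0.05; equal arms; n per arm 10, 20 or 30; SD of change 7, 5 or 3 letters; true effect zero; scoring adds b letters on average to one arm's change.

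**Formula.** SE = SD × √(2/n); noncentrality δ = b / SE; df = 2n − 2. The false-positive rate is the probability that a noncentral t with these values exceeds the two-sided 5% critical value in either direction.

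Example: n = 20, SD = 5, b = 1. SE = 5 × √(2/20) = 1.581; δ = 1/1.581 = 0.632; df = 38; rejection rate 9.5%.

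| n per arm, SD | SE | b = 0 | b = 0.5 | b = 1 | b = 2 | Smallest significant difference |
|---|---|---|---|---|---|---|
| 10, SD 7 | 3.130 | 5.0% | 5.3% | 6.1% | 9.3% | 6.58 letters |
| 20, SD 5 | 1.581 | 5.0% | 6.1% | 9.5% | 23% | 3.20 letters |
| 30, SD 3 | 0.775 | 5.0% | 9.7% | 25% | 72% | 1.55 letters |

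The b = 0 column is the benchmark when scoring does not depend on arm.

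**What size of b is plausible?** Suppose a line has 5 letters and each urged guess is right with probability 0.1 to 0.3 (both assumed). One extra line adds 5 × 0.1 = 0.5 to 5 × 0.3 = 1.5 letters; two extra lines add 1 to 3. These are gains per person urged. If only half of one arm, and nobody in the other, gets one extra line at the final test, the mean differential is 0.5 × 0.5 = 0.25 to 0.5 × 1.5 = 0.75 letters. A mean differential of 2 letters needs, for example, two extra lines at probability 0.2 (10 × 0.2 = 2) for everyone in one arm and nobody in the other.

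**Reading.** With few participants and noisy scores the rate stays near nominal. With more participants and a small SD, even 1 letter matters. The calculation covers acuity only.

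**The case against.** The strongest reply is that acuity, the primary outcome, is already fairly well controlled. The plan adopts an established procedure, gives an opening script, sets a floor of three missed letters, refuses corrections once the next letter is read, and has wrong responses written down. Both arms are assessed in the same way, and balance training is an active comparator. The differentials that do real damage require systematic over-urging of nearly a whole arm at the final visit only. A fixed stop would also depart from a known procedure, and under effective masking the remaining discretion adds noise rather than bias.

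Much of this stands as a limit on size. It does not close the gap. None of these features limits how often the examiner urges or conceals the arm. Balance training acts on participants, not on the examiner, and applying the same procedure to both arms does not help where the procedure itself contains discretion. The argument that discretion is harmless under masking presupposes masking that the plan does not describe.

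Four stronger readings are tempting, and the documents do not support them:

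- That the examiner is unmasked. The plan is silent; it does not say the examiner knows the arm.
- That acuity testing permits hints. The optional coaching belongs to the contrast test only.
- That the plan claims to exclude psychological explanations. It says only that a difference would suggest physiological ones.
- That a separate vision tester already exists. Sessions are monitored by a fitness specialist and blood is drawn by a phlebotomist, but nobody is named for vision testing.

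**Conclusion.** The concern holds as a gap in the plan. No examiner masking is described, the primary letter count depends partly on examiner judgement, and the final count is taken when the arm is easily learned (an inference from the timing, not a statement in the documents). Arm-dependent urging at that visit would pass into the change score, so the suggestion that a difference points away from test-specific psychological causes lacks support from the design.

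For differentials of 0.5 to 2 letters, the false-positive rate runs from 5.3% to 72% across the scenarios shown, against 5%. All of n, SD, alpha and b are assumed. A reader might infer from the upper end that a positive result would be spurious, or that the bias must favour exercise. Neither follows, because the direction and size of any bias are unknown. The inferential gap does not depend on the size. The changes below are worth making as a cheap improvement.

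**What to change.** 1. For every subject and visit, require one response to each letter. Stop acuity testing at the end of the first line with three or more misses, and contrast testing at the first triplet with two or more misses.
2. Use one fixed set of prompts for each test, and drop the optional hints for contrast.
3. Where existing staffing allows, have vision tested by someone who does not run the sessions and is not told the arm. Test away from the training area, since the final measurement follows a session, and ask participants not to mention their group.
4. Unless masking is kept, remove or qualify the sentence under Expected outcomes and Significance that contrasts physiological with psychological causes.

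Items 1, 2 and 4 need wording only and no staff. Item 3 needs scheduling and depends on who is available, which the documents do not show. The price is less freedom to coax hesitant readers and slightly less comparability with the test instructions as now written.

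### The acuity analysis does not say which visit is its baseline, and no stated comparison uses the 3-month acuity

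*Combined protocol and SAP*

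**What the plan says.** The Specific Aim is to assess visual outcomes and serum BDNF "before, during, and after an aerobic exercise training program that includes progressive increases in exercise". Visual acuity is the primary outcome.

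The Design describes a "12-week exercise portion with one return visit 3 months after the end of the exercise portion", with participants asked to go back to their usual habits once training ends. On timing it states: "Blood draws and visual assessments will be taken at one week prior to the 12-week regimen, at the 3-month follow-up". Four more assessments are listed as falling within the regimen itself, in weeks 1, 4, 8 and 12. That makes six visual assessments. Timing within a session is given for blood only: "Blood will be drawn by a certified phlebotomist in the rest period before the exercise, immediately following the exercise", and again after a short recovery. No such timing is given for vision.

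The Statistical analysis paragraph under Visual acuity uses two of these readings. The ETDRS letter count "assessed prior to start of the first session of the the 12 week study is subtracted from the number of correct responses" at the end of the last session, and the two group means of this difference are compared by two-tailed t-test. No other visual analysis is stated.

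**The concern.** Two things are left open in the analysis of the primary outcome.

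**Baseline.** A reading taken one week before the regimen and a reading taken in week 1 just before the first session both satisfy the analysis wording. The choice between them, or between either one and their average, could therefore be made after the data are seen. If both exist, using only one also gives up precision that the schedule already pays for.

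**3-month visit.** This is the only visual assessment made after training has stopped, so it is the only one that can show whether a change in acuity lasts or reverses. With no comparison planned, any statement on persistence would rest on an analysis chosen afterwards.

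**Working it through.** The documents give no sample size, power, SD or between-visit correlation, so there is no figure of the plan's own to reproduce. The check has two parts.

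**1. Schedule against analysis**

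| Visual assessment (Design) | Relation to training | Role in the stated analysis |
|---|---|---|
| One week before | Before, for certain | Possible baseline |
| Week 1 | Within the regimen; before or after exercise not stated | Possible baseline, only if tested before the first session |
| Weeks 4 and 8 | During | None |
| Week 12 | End of training | End value, on the natural reading of last session |
| 3-month follow-up | After | None |

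Two of the six assessments are used and 6 - 2 = 4 are not. The Design uses the word session for training and calls the 3-month contact a return visit, so the last session most naturally falls in week 12. If it meant the 3-month visit instead, the end-of-training value would be the one left without an analysis. On either reading, one of the two time points has none.

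**2. What a second baseline would be worth, if there is one**

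Assume that each test has error variance s² (s = test-retest SD), that errors are independent across visits, and that the true change varies between people with SD t. Neither s nor t is in the documents.

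- Change from one baseline: t² + s² + s² = t² + 2s².
- Change from the mean of two baselines: t² + s² + s²/2 = t² + 1.5s².

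| Assumed t | Variance ratio | Reduction | Equivalent extra participants (1/ratio - 1) |
|---|---|---|---|
| 0 | 1.5/2 = 0.75 | 25% | 33% |
| s | 2.5/3 = 0.833 | 17% | 20% |
| 2s | 5.5/6 = 0.917 | 8% | 9% |

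A second model, with equal SD at each visit and equal correlation rho between all visits, gives change-score variances of 2(1 - rho)SD² and 1.5(1 - rho)SD². The ratio is again 0.75 at every rho, which matches the t = 0 row, the most favourable one.

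The gain depends on timing. If the week-1 test followed some training and the groups already differed by g letters, averaging it into the baseline would subtract g/2 from the estimated group difference. Averaging is therefore sound only if the week-1 test is fixed before the first session.

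**The case against.** A reader might go further than the documents allow in three ways.

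- *A second pre-training reading is being wasted.* Only the visit one week before is documented as untrained. Week 1 lies inside the regimen, training is three times a week, and vision has no stated timing within the session. A second untrained reading is plausible but not established.
- *The trial cannot say what happens after training.* Acuity is scheduled at 3 months for both groups and could be compared in the same way. What is missing is a prespecified comparison, not the data.
- *Persistence of visual benefit is the sole purpose of the 3-month visit.* Blood is drawn there too, and the documents state no such purpose.

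Beyond this, change from a single baseline is a valid and conventional analysis, so the precision argument shows an improvement and not an error. Baseline adjustment would also gain precision without moving any test. Under the equal-correlation model with one baseline, the variance (1 - rho²)SD² is 0.75, 0.51 and 0.19 times SD² at rho 0.5, 0.7 and 0.9, against 1.0, 0.60 and 0.20 for the change score. That is 25%, 15% and 5% less. This stands as an alternative, but it still needs a named baseline visit.

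Finally, the conclusion planned under Expected outcomes concerns benefit from short-term exercise and makes no claim of persistence, and the end-of-training reading could be said to serve part of the after element of the aim. The first point stands and limits the seriousness. The second is weak: a reading at the close of the last session shows the state when training ends, not after it has been stopped.

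**Conclusion.** The concern holds in limited form. The baseline of the primary outcome is not tied to a visit, and no stated comparison uses the 3-month acuity, so the plan as written leaves the post-training part of its aim without an analysis. Both follow from the text and need no assumption, except that the last session is read as falling in week 12.

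The precision gain is conditional. It exists only if week-1 vision is tested before the first session, and it is 25%, 17% or 8% of change-score variance at t = 0, s or 2s, given independent test errors of equal variance. A practice effect common to both groups would largely cancel in the between-group comparison. The primary test can run as planned; the change is worth making because it is cheap and removes choices that would otherwise be made after the data are seen.

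**What to change.** Amend the Statistical analysis paragraph under Visual acuity, and the visit timing in the Design to match:

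1. Hold the week-1 visual test before the first session in both groups, and define baseline as the mean of the letter counts from that test and the visit one week before the regimen.
2. Name week 12 as the primary time point and keep its between-group comparison as primary.
3. Add one prespecified secondary between-group comparison: 3-month letter count minus the same baseline, with a 95% confidence interval. State that persistence is claimed only from this comparison.

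The cost is some wording, one extra comparison on data already scheduled, and a fixed time for the week-1 visual test in both groups. No visit or test is added. The downside is less scheduling freedom in week 1 and the loss of a week-1 visual reading on training; weeks 4 and 8 still cover the training period.

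This does not supply an analysis for weeks 4 and 8 or for contrast sensitivity, the secondary outcome. Neither has one in the document, and both need separate attention.

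### The primary acuity change compares a score taken before the first session with one taken after the last, so any acute spin-minus-balance effect counts as a training effect

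*Combined protocol and SAP*

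**What the plan says.** The Objectives make acuity the main endpoint: "To assess changes in visual acuity (primary outcome) and contrast sensitivity (secondary outcome").

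The statistical analysis paragraph under Visual acuity (Methods, Visual function testing) defines the change score. The baseline count is "assessed prior to start of the first session", and it "is subtracted from the number of correct responses elicited at the end of the last session of the study". Mean changes in the balance-training and aerobic-exercise arms are compared by a two-tailed t-test.

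The Design paragraph shows what a session is: "Exercise time will progress from an initial 20 minutes per session", rising to at most 45 minutes. The return three months after the programme is called a visit. Vision testing is scheduled by week only: "Blood draws and visual assessments will be taken at one week prior to the 12-week regimen", then in weeks 1, 4, 8 and 12 and at the 3-month follow-up. Timing around the bout (before, immediately after, after 10 minutes of recovery) is given for blood only. Controls take part in group balance training and "undergo other assessments identically to the exercised participants".

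Under Expected outcomes and Significance, if functional changes differ between the arms, "we will conclude that even relatively short-term aerobic exercise can be beneficial to visual health".

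**The concern.** The two ends of the primary change score are taken in different states. No session precedes the baseline measurement, whereas the final one, read plainly, comes straight after a bout of up to 45 minutes. Nothing else in the documents matches the states: there is no rest interval before the final acuity test and no pre-session acuity test on the last day.

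The balance-training control removes only the acute effects that both session types share. It is there to control for benefits unrelated to aerobic exercise, so an acute aerobic effect is precisely what it would leave in.

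At stake is the meaning of the primary result. The plan would read a group difference as a benefit of a short aerobic training programme. With unmatched states, the test cannot separate a lasting training effect from a same-day effect of the last session. The bias could run either way, creating a difference or hiding a real one.

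**Working it through.** **Inputs from the documents.** Baseline before the first session, final score at the end of the last session, two-arm comparison of mean change, two-tailed t-test (acuity statistical analysis paragraph); balance-training control assessed identically (Design). The documents state no alpha, SD, sample size or effect size, so there is no figure of the plan's own to reproduce.

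**What the test estimates.** Let T be an arm's training effect and A the acute effect of its last session on acuity. No session precedes baseline, so the expected change in an arm is T + A, and the contrast is

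(T_spin − T_balance) + (A_spin − A_balance).

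The second bracket is the bias, letter for letter. It is zero if the acute effects are equal. If both scores are taken before a session, A drops out and only T_spin − T_balance remains. A simulation with no training effect and assumed A_spin = 2 and A_balance = 0.5 letters gave a contrast of 1.5 letters with the documented timing and 0.0 with matched timing.

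**Illustration of size (all inputs assumed).** SD of change 5 letters, n = 20 per arm, two-sided alpha 0.05, T_spin = T_balance, net acute difference d letters.

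- Standard error of the contrast: 5 × √(2/20) = 1.58 letters.
- Degrees of freedom: 2 × 20 − 2 = 38; critical t = 2.024.
- Noncentrality: d / 1.58.
- Chance of a significant result: P(|t| > 2.024) under the noncentral t.

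| d (letters) | Noncentrality | SD 5, n = 20 | Lowest (SD 6, n = 10) | Highest (SD 4, n = 30) |
|---|---|---|---|---|
| 0 | 0 | 5.0% | 5.0% | 5.0% |
| 0.25 | 0.16 | 5.3% | – | – |
| 0.5 | 0.32 | 6.1% | – | – |
| 1 | 0.63 | 9.5% | 6.4% | 15.9% |
| 2 | 1.26 | 23.4% | 10.9% | 47.8% |
| 3 | 1.90 | 45.6% | 18.5% | 81.5% |

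The last two columns are the extremes over SD 4 to 6 and 10 to 30 per arm. A simulation of 100,000 trials at SD 5, n = 20 gave 9.4%, 23.5% and 45.6% for d = 1, 2 and 3, and 5.0% when an acute effect of 2 or 3 letters was the same in both arms.

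The false-positive rate doubles to 10% at d = 1.06 letters (0.69 at SD 4, n = 30; 1.85 at SD 6, n = 10).

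**Masking.** Assume a true training effect of 4 letters (SD 5, n = 20). Power is 69.3% with no net acute effect. A net acute effect of −1, −2 or −3 letters leaves a contrast of 4 − 1 = 3, 4 − 2 = 2 or 4 − 3 = 1 letter, and power of 45.6%, 23.4% or 9.5%.

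**The case against.** The strongest counter-argument is about wording. The sentence may only be naming the start and end of the programme, loosely. That is possible. But the text places the final test after a session, and the Design paragraph uses the word for exercise bouts. On the loose reading the test state of the primary final score is simply not stated, and the same sentence is needed to fix it.

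A second argument is that the baseline state is also unsettled. The Design paragraph schedules blood and vision together one week before the regimen and describes blood draws around exercise without exempting that visit. This is an inference from a sentence about blood; the acuity analysis itself places the baseline before any session.

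Third, no acute effect on acuity is shown, shared effects such as arousal or retesting cancel, and the error rates above would follow from any additive bias of the same size. All of this stands. The rates show how sensitive the test is, not how large the problem is, and at a net effect of 0.25 or 0.5 letters the rate stays close to nominal.

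Finally, acuity is also collected at weeks 1, 4 and 8 and at the 3-month visit, which could help show whether a difference persists. No acuity analysis using those data is specified, so they do not protect the primary test.

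**Conclusion.** The concern holds. As written, the primary contrast equals the training difference plus the net acute effect of the last spin session over the last balance session, and nothing in the plan removes the second term. The decomposition needs only the plain reading of the word session. Whether a net acute effect on acuity exists, how large it is and which way it runs are unknown, so no actual bias is demonstrated and the percentages rest wholly on assumed inputs. Confidence is moderate, because the sentence can be read loosely. It should be fixed, because it is a stated rule for the primary outcome that can give a wrong answer in either direction and the correction costs almost nothing.

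**What to change.** In the acuity statistical analysis paragraph, define the final primary score as the letter count at the week-12 assessment, tested at rest before that day's session, in the same state as the baseline, for both arms. If a post-session acuity score is wanted, keep it as a separate exploratory outcome. Stating the same pre-session timing for contrast sensitivity and for weeks 1, 4 and 8 would be consistent but is optional, since no mismatch is stated there.

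The cost is one sentence and a change in the order of procedures at the week-12 visit, with no extra visit, staff or test. If week-12 testing has already been done, the report should say when within the visit acuity was measured and, if it followed the session, limit the conclusion accordingly.
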